2.2 Secondary Objectives

1. To determine the MRD-negative rate after ASCT
2. To evaluate the toxicity, response rate, PFS, and OS of IRD consolidation
3. To collect pilot data to compare toxicity, response rate, PFS, OS, and the rate of MRD-positive to MRD-negative conversion between the two maintenance arms
4. To evaluate the association of PFS and OS with MRD-negativity and MRD-positivity prior to consolidation and after 4 cycles of IRD consolidation

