3.0 PATIENT SELECTION

3.1 Inclusion Criteria

Each patient must meet all of the following inclusion criteria to begin IRD Consolidation

1. Between the ages of 18 and 70 years of age (inclusive) at time of enrollment
2. Voluntary written consent must be given before performance of any study-related procedure not part of standard medical care, with the understanding that consent may be withdrawn by the patient at any time without prejudice to future medical care.
3. Histologically confirmed diagnosis of symptomatic multiple myeloma. (Patients with multiple myeloma with secondary amyloidosis are eligible.)
4. Received at least two cycles of any regimen as initial systemic therapy for multiple myeloma and are within 2-16 months of the first dose of initial therapy
5. Eastern Cooperative Oncology Group (ECOG) performance status and/or other performance status 0, 1, or 2 (see Appendix A).
6. Adequate organ function as defined below:
 - Absolute neutrophil count (ANC) $\geq 1,000/\text{mm}^3$.
 - Platelet count $\geq 75,000/\text{mm}^3$; platelet transfusions to help patients meet eligibility criteria are not allowed within 7 days before study enrollment.
 - Total bilirubin $\leq 1.5 \times$ the upper limit of the normal range (ULN).
 - Alanine aminotransferase (ALT) and aspartate aminotransferase (AST) $\leq 3 \times$ ULN.
 - Calculated creatinine clearance ≥ 30 mL/min (see Appendix B).
7. Women of childbearing potential (as defined in Section 5.6) must follow pregnancy testing requirements as outlined in the Revlimid REMS® program material. This is defined as either committing to continued abstinence from heterosexual intercourse or beginning TWO acceptable methods of contraception (one highly effective method and one additional effective method (as defined in Section 5.6) AT THE SAME TIME) at least 28 days prior to the start of lenalidomide, for the duration of study participation, and for 28 days following the last dose of lenalidomide. Women of childbearing potential must also agree to ongoing pregnancy testing.
8. Men must agree to use a latex condom during sexual contact with a woman of childbearing potential even if they have had a successful vasectomy. All patients must be counseled at a minimum of every 28 days about pregnancy precautions and risks of fetal exposure. Should a woman become pregnant or suspect she is pregnant while participating in this study, she must inform her treating physician immediately.

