3.2 Exclusion Criteria

Patients meeting any of the following exclusion criteria are not to be enrolled in the study:

1. Female patients who are lactating or have a positive serum pregnancy test during the screening period.
2. Evidence of MM disease progression any time prior to enrollment. Progression from smoldering/asymptomatic MM to symptomatic MM is not exclusionary.
3. Tandem autologous transplantation
4. History of plasma cell leukemia or MM CNS involvement.
5. Administration or planned administration of any other concomitant chemotherapy, immunotherapy, radiotherapy, or any ancillary therapy which would be considered a treatment of multiple myeloma until Day +28 post-transplant through discontinuation from study. Patients may be on corticosteroids if they are being given for disorders other than multiple myeloma (e.g., adrenal insufficiency, rheumatoid arthritis, etc.).
6. Any serious medical or psychiatric illness that could, in the investigator's opinion, potentially interfere with the completion of treatment according to this protocol.
7. Prior organ transplant requiring immunosuppressive therapy.
8. Active hepatitis A, B or C virus infection, or known human immunodeficiency virus (HIV) positive.
9. Known allergy to any of the study medications, their analogues, or excipients in the various formulations of any agent.
10. Known GI disease or GI procedure that could interfere with the oral absorption or tolerance of ixazomib.
11. Concurrent hematologic or non-hematologic malignancy requiring treatment (other than multiple myeloma and secondary amyloidosis).
12. Cardiac syncope, uncompensated NYHA Class 3 or 4 congestive heart failure (Appendix C), myocardial infarction within the previous 6 months, unstable angina pectoris, clinically significant repetitive ventricular arrhythmias despite antiarrhythmic treatment, severe orthostatic hypotension, or clinically important autonomic disease.
13. Grade \geq 3 peripheral neuropathy, or Grade 2 with pain on clinical examination during the screening period.
14. Major surgery within 14 days prior to start of study treatment.
15. Infection requiring systemic antibiotic therapy or other serious infection within 14 days prior to start of study treatment.

16. Participation in other clinical trials, including those with other investigational agents not included in this trial, within 30 days prior to start of study treatment and throughout the duration of this trial.

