5.0 TREATMENT PLAN

5.1 Overview

In general, patients will provide informed consent prior to ASCT. However, patients may be allowed to provide informed consent following ASCT, determined on a case-by-case basis by the PI. In this event, any of the assessments required prior to ASCT not performed for SOC will not be required.

Patients will undergo standard of care ASCT with conditioning regimen determined by the treating physician per institutional guidelines. The ASCT is not considered part of this study. Consolidation therapy will begin on between Day 80 and Day 120 following ASCT and will consist of four 28-day cycles of IRD (ixazomib, lenalidomide, & dexamethasone). Barring dose modifications for toxicity, 4 mg of ixazomib and 40 mg of dexamethasone will be administered on Days 1, 8, and 15, and 15 mg of lenalidomide will be administered on daily on Days 1-21.

Following completion of consolidation therapy, patients will undergo restaging and will be randomized on a 1:1 basis to maintenance therapy with ixazomib or lenalidomide. Patients will be stratified based on MRD status at restaging (MRD-positive v. MRD-negative). Patients who discontinue either ixazomib or lenalidomide during the consolidation phase due to toxicity will not be randomized. They will be preferentially enrolled on the opposing arm.

Barring dose modifications for toxicity, ixazomib maintenance will consist of 4 mg administered on Days 1, 8 and 15 of each 28-day cycle, and lenalidomide maintenance will consist of 10 mg daily on Days 1-28 for the first three 28-day cycles and 15 mg daily for all further cycles. Maintenance therapy with either ixazomib or lenalidomide will continue until the patient experiences disease progression or unacceptable toxicity.

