12.1.2 Complete Response

Complete response (CR) requires all of the following:

- Disappearance of monoclonal protein by both protein electrophoresis and immunofixation studies from the blood and urine
- If serum and urine monoclonal protein are unmeasurable, Normal free light chain ratio (0.26-1.65)
- <5% plasma cells in the bone marrow
- Disappearance of soft tissue plasmacytoma

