12.1.4 Partial Response

Partial response (PR) requires all of the following:

- $\geq 50\%$ reduction in the level of the serum monoclonal protein
- Reduction in urine monoclonal protein by either $\geq 90\%$ or to < 200 mg
- If serum and urine monoclonal protein are unmeasurable, a $\geq 50\%$ decrease in difference between the involved and uninvolved free light chain levels is required in place of monoclonal protein criteria (The absolute decrease must be > 10 mg/dl)
- If serum and urine monoclonal protein are unmeasurable and serum free light chain is unmeasurable, a $\geq 50\%$ reduction in plasma cells is required in place of monoclonal protein, provided that baseline bone marrow plasma cell percentage was $\geq 30\%$
- If present, > 50% reduction in the size of soft tissue plasmacytomas (by clinical or radiographic examinations).

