15.3 Data Analysis

For the analysis of consolidation therapy, the data for safety analysis will include these patients who have at least 1 dose of IRD consolidation therapy, while the data for efficacy analysis will include patients who complete 4 cycles therapy. Demographic and clinical characteristics of the sample, as well as adverse events, complications and loss to follow-up will be summarized using descriptive statistics. The change of MRD-negative rates for pre- and post-consolidation therapy will be described using contingency table and compared by McNemar test. The incidences of mortality, progression, relapse, as well as tumor response (complete response and overall) and their 95% confidence intervals following consolidation therapy will also be calculated.

Data analysis for maintenance portion will be performed following the intent-to-treat (ITT) principle. The balance of demographic and baseline clinical characteristics between two arms will be compared using t-test, Mann-Whitney rank-sum test, or Chi-square test as appropriate. The distributions of responses and adverse events across two arms will be summarized using contingency tables and compared by 2-sample Chi-square test or Fisher's exact test. Contingency table and Fisher's exact test will also be used to assess the between-arms difference for the rates of conversion from MRD-positive to MRD-negative. Chi-square test will be used to compare the distribution of responses, and Kaplan-Meier curves with log rank tests will be used to compare PFS and OS.

Overall survival (OS) will be defined as time from ASCT to death due to any causes, and survivors will be censored at withdrawal or study closeout. Progression-free survival (PFS) will be defined as time from ASCT to progression, relapse, or death, whichever occurs first, and those event-free survivors will be censored at withdrawal or study closeout. The between-arm differences in OS and PFS will be described using Kaplan-Meier product limit estimator and compared by log-rank tests. Kaplan-Meier curves will also be used to describe the association between MRD status (both prior to and after consolidation therapy) and OS or PFS, and proportional hazards Cox models will be used to control the potential confounding effects of other patient and clinical characteristics.

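### The planned CR rate after consolidation counts CRs already present before IRD, and overall response has no stated reference time point

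*Combined protocol and SAP*

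**What the plan says.** Section 2.2 sets the objective: "To evaluate the toxicity, response rate, PFS, and OS of IRD consolidation". Section 15.3 gives the only response analysis for this phase: "as well as tumor response (complete response and overall) and their 95% confidence intervals following consolidation therapy will also be calculated". It plans no response rate before IRD, no change, no upgrade rate and no comparator. The analysis set is restricted: "the data for efficacy analysis will include patients who complete 4 cycles therapy".

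Patients arrive already treated. Section 3.1 requires: "Received at least two cycles of any regimen as initial systemic therapy for multiple myeloma". Section 5.1 places IRD after transplant: "Consolidation therapy will begin on between Day 80 and Day 120 following ASCT". Section 3.2 excludes: "Evidence of MM disease progression any time prior to enrollment".

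Section 12.1.2 defines CR by the absence of disease markers, beginning with: "Disappearance of monoclonal protein by both protein electrophoresis and immunofixation studies from the blood and urine". Section 12.1.4 defines PR by change, requiring at least a 50% "reduction in the level of the serum monoclonal protein". Section 12.1.3 allows VGPR through a 90% reduction as one of two routes. Neither section says from which time point a reduction is counted.

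For MRD, Section 15.3 does plan a paired comparison before and after consolidation, by contingency table and McNemar test.

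**The concern.** The objective concerns what happens with IRD, whereas the planned figure describes where patients stand after induction, ASCT and IRD together. Because CR is a state, a patient in CR at the pre-consolidation visit who is still in CR at restaging adds one to the numerator. The proportion cannot separate that patient from one who converted during IRD.

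The protocol itself expects deep responses before the first IRD dose: Section 15.1 assumes about 50% MRD-negativity at Day 100 after transplant. That is not a CR rate, but it makes pre-existing CR a practical matter.

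At stake is the reading of a secondary endpoint. A rate reported against the wording of objective 2 would invite the reader to credit IRD with responses obtained earlier.

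**Working it through.** The plan gives no target, power or sample size for response, so there is no figure of its own to reproduce.

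**Inputs**
- n = 220, the evaluable accrual goal in Section 15.0, taken here as the size of the response analysis.
- CR rate before IRD: not in the documents. Assumed 20% to 60%.
- Share of all patients losing CR during IRD: assumed 2% in the paired illustration.
- Overall response: not defined in Section 15.3. Taken as PR or better.

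**Step 1: the planned estimate when nobody's CR status changes.** The rate after IRD then equals the rate before it. The exact (Clopper-Pearson) 95% limits for x of n are the 2.5% quantile of Beta(x, n − x + 1) and the 97.5% quantile of Beta(x + 1, n − x).

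| CR before = CR after | x of 220 | 95% CI |
|---|---|---|
| 20% | 44 | 14.9 to 25.9 |
| 30% | 66 | 24.0 to 36.5 |
| 40% | 88 | 33.5 to 46.8 |
| 50% | 110 | 43.2 to 56.8 |
| 60% | 132 | 53.2 to 66.5 |

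Any of these could be reported with no conversion at all.

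**Step 2: one planned result, three different histories.** Fix the observed rate at 110/220 = 50%. Let g be the share of all patients who gain CR and l the share who lose it. The paired change is d = g − l, with SE = √((g + l − d²)/n) and 95% CI d ± 1.96 × SE.

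- g = 0.02, l = 0.02: SE = √(0.04/220) = 0.0135
- g = 0.12, l = 0.02: SE = √((0.14 − 0.01)/220) = 0.0243
- g = 0.22, l = 0.02: SE = √((0.24 − 0.04)/220) = 0.0302

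| CR before | CR after, as planned (95% CI) | Paired change, points (95% CI) | Conversion among those not in CR before |
|---|---|---|---|
| 50% | 50% (43.2 to 56.8) | 0 (−2.6 to +2.6) | 2/50 = 4% |
| 40% | 50% (43.2 to 56.8) | +10 (+5.2 to +14.8) | 12/60 = 20% |
| 30% | 50% (43.2 to 56.8) | +20 (+14.1 to +25.9) | 22/70 = 31% |

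The planned column is constant. The paired change and the conversion rate distinguish the three cases.

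**Step 3: overall response.** If reductions are counted from diagnosis, falls achieved by induction and ASCT qualify. If they are counted from the pre-consolidation value, PR does measure change during IRD, but a patient with no measurable M-protein left has nothing to reduce. The text of Section 12.1 does not choose between these, so no size can be given.

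**Step 4: are the data there?** The calendar in Section 8.0 schedules serum electrophoresis and immunofixation, free light chains, urine studies, plasmacytoma assessment and marrow both at the pre-consolidation visit (within 28 days before C1D1) and at restaging. Note 9 requires repeat urine only in patients with at least 200 mg/24h of M-protein at screening. Section 10.0 lists a Response Form for each treatment cycle but none among the baseline forms. The components of CR are therefore scheduled, but the pre-consolidation category is not shown to be recorded.

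**The case against.** The strongest reply is that the trial already measures change over IRD where it counts. The primary objective is improvement in MRD-negativity, analysed as a paired comparison, and the sample size rests on it. Response is a descriptive secondary endpoint, and Section 15.3 refers to a time after consolidation without claiming an IRD effect. This stands, and it limits the point to the response endpoint. It does not supply the missing CR comparison: the general descriptive summary of clinical characteristics could show response before IRD, but the plan does not promise it.

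A second reply is that Section 12.1 relies on the IMWG criteria, which may settle the reference time point. The protocol text does not, and with induction, ASCT and IRD in sequence the choice needs to be written down.

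A reader might infer more than the documents support:
- *That most patients already hold a response before IRD.* Only progression is excluded. Stable disease is eligible, and no minimum response is required.
- *That overall response measures the whole prior course.* That holds under one reference time point and not under another, and none is stated.
- *That a paired analysis would show what IRD added.* There is no concurrent control, so it cannot be separated from continued deepening of response after ASCT.
- *That a later phase III design would be misled.* No decision rule or sizing in the plan uses CR or overall response.
- *That the maintenance response comparison has the same fault.* Those arms are randomised with stratification by MRD status, so comparing their response distributions is legitimate.

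**Conclusion.** The point holds for CR without outside assumptions. The definition is a state, every patient has had prior induction and ASCT, and only the proportion after consolidation is planned, so that proportion carries no information on change during IRD. In the illustration, one result of 50% (43.2 to 56.8) fits a change of 0, +10 or +20 points. Those sizes rest on assumed CR rates before IRD, an assumed 2% loss of CR and n = 220.

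For overall response the finding is narrower: the estimand is undetermined until a reference time point is stated. The primary MRD analysis is untouched. This is a worthwhile correction to a secondary endpoint and does not threaten the trial's main conclusion. Because efficacy is analysed in four-cycle completers, both the planned proportion and a paired change in that set describe completers only.

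**What to change.** Amend Section 15.3 for secondary objective 2:

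- (a) Assign CR/sCR status at the pre-consolidation visit and at restaging from the assessments already in the calendar. Report the paired before/after table, the change in CR/sCR rate with its 95% CI, and the McNemar test. Apply the same rule at both visits where urine was not repeated under note 9.
- (b) Report conversion to CR among patients not in CR before consolidation.
- (c) Label the proportions after consolidation as cumulative response after induction, ASCT and IRD. State the reference time point for PR and VGPR in Section 12.1.
- (d) Report a paired change in VGPR or better only where a diagnosis M-protein value is available.
- (e) Describe the paired results as change during consolidation.

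The cost is one extra table and recording a pre-consolidation response category, which Section 10.0 does not list at baseline. Items (a) and (b) need no diagnosis value. Item (d) does, and the documents do not show that it is collected: the earliest calendar sample is Day −60 to Day −2 before ASCT, and patients who consent after ASCT may lack even that. Some values would have to be abstracted from records, with some missing.

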5.3.2 Ixazomib Administration

Ixazomib will be prescribed only to eligible patients under the supervision of the investigator or identified sub-investigator(s). Ixazomib will be administered on Days 1, 8, and 15 of a 28-day cycle at a starting dose of 4 mg. Sufficient quantity of drug for one cycle of therapy will be prescribed to the patient in Cycles 1-3 of maintenance therapy, and for three cycles of therapy in Cycles 4+.

Patients should be monitored for toxicity, as necessary, and doses of ixazomib should be modified as needed to accommodate patient tolerance to treatment; this may include symptomatic treatment, dose interruptions, and adjustments of ixazomib dose (see Section 6.0). Once ixazomib is reduced for toxicity, no dose re-escalation is permitted.

Ixazomib should be taken on an empty stomach (no food or drink), at least 1 hour before or 2 hours after a meal. Patients should be instructed to swallow ixazomib capsules whole and not to break, chew, or open the capsules. Each capsule should be swallowed separately with a sip of water. A total of approximately 8 ounces (240 mL) of water should be taken with the capsules.

Ixazomib should be taken at the same time each day. Missed doses can be taken as soon as the patient remembers if the next scheduled dose is 72 hours or more away. A double dose should not be taken to make up for a missed dose. Patients who vomit a dose after ingestion will not receive an additional dose, but should resume dosing at the time of the next scheduled dose.

If ixazomib maintenance is discontinued, crossover to the lenalidomide maintenance arm can occur if permission is granted by the Principal Investigator. Patients who crossover will continue to be followed per all protocol guidelines.

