5.3.3 Lenalidomide Administration

Lenalidomide will be prescribed only to eligible patients under the supervision of the investigator or identified sub-investigator(s). Lenalidomide will be administered daily continuously for a 28-day cycle at a starting dose of 10 mg. If lenalidomide is tolerated well (i.e. no dose modification required) during the first three cycles, lenalidomide dose will be increased to 15 mg daily. Sufficient quantity of drug for one cycle of therapy will be prescribed to the patient in Cycles 1-3, and for three cycles of therapy in Cycles 4+. Lenalidomide will be provided in accordance with the Celgene Corporation's Revlimid REMS® program.

VTE prophylaxis is not required during single-agent lenalidomide maintenance but is permissible at the discretion of the treating physician.

Patients should be monitored for toxicity, as necessary, and doses of lenalidomide should be modified as needed to accommodate patient tolerance to treatment; this may include symptomatic treatment, dose interruptions, and adjustments of lenalidomide dose (see Section 6.0).

If a lenalidomide dose reduction has occurred for hematologic toxicity and ANC $>1000/\mu\text{L}$ and platelet count is $>75,000/\mu\text{L}$, lenalidomide drug dose may be re-escalated one dose level per cycle to a maximum of 15 mg daily. If lenalidomide was reduced due to non-hematologic toxicity, no dose re-escalation is permitted.

Lenalidomide can be taken without regards to food or drink. Patients should be instructed to swallow lenalidomide capsules whole and not to break, chew, or open the capsules. Each capsule should be swallowed separately with a sip of water.

Lenalidomide should be taken at the same time each day. Missed doses can be taken as soon as the patient remembers if the next scheduled dose is 8 hours or more away. A double dose should not be taken to make up for a missed dose. Patients who vomit a dose after ingestion will not receive an additional dose, but should resume dosing at the time of the next scheduled dose.

If lenalidomide maintenance is discontinued, crossover to the ixazomib maintenance arm can occur if permission is granted by the Principal Investigator. Patients who crossover will continue to be followed per all protocol guidelines.

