8.0 STUDY CALENDAR

Please note that all assessments allow a window of +/-3 days for scheduling issues.

	Screening		Consolidation ³			Restaging ⁴	Maintenance ⁵			EOS ⁷	F/U ⁸
	Prior to ASCT ¹	Prior to beginning consolidation ²	D1	D8	D15		D1	D8	D15		
Informed consent	X										
H&P, ECOG PS, plasmacytoma assessment	X	X	X ¹³			X	X ^{13,14}			X	X ¹⁵
CBC & CMP	X		X ¹³		X ⁶	X	X ^{13,14}			X	
SPEP and immunofixation	X	X	X ¹³			X	X ^{13,14}			X	
24h urine for total protein, UPEP, and immunofixation ⁹	X	X	X ¹³			X	X ^{13,14}			X	
Serum-free light chains & β2 microglobulin	X	X	X ¹³			X	X ^{13,14}			X	
Quantitative immunoglobulins (IgA, IgG, IgM)	X	X	X ¹³			X	X ^{13,14}			X	
Serum βhCG ¹⁰	X	X	X				X			X	
Bone marrow biopsy and aspirate ¹¹	X	X				X	X ¹⁶				
Central labs ¹² (MRD Analysis)		X				X	X ¹⁶				
Central labs ¹² (Hevylite)	X		X ¹³			X	X ^{13,14}			X	
Central labs ¹⁸ (Sub-study)		X ¹⁸					X ¹⁸				
Ixazomib			X	X	X		X	X	X		
Lenalidomide			Days 1-21				Days 1-28				
Dexamethasone			X	X	X						
Administration Questionnaire ¹⁷			X				X				
Adverse events assessment			X ----- X								

1. Day -60 to Day -2

2. Day +80 to Day +120; to occur within 28 days prior to C1D1 of consolidation

3. 4 28-day cycles

4. Prior to beginning maintenance (approx. Day +192 to Day +232); to occur within 28 days after completing C4 of consolidation and within 28 days prior to C1D1 of maintenance

5. 28-day cycles; continued until progression or unacceptable toxicity

6. Cycles 1-2 only

7. Within 30 days of last dose of study drug(s)

8. Every 3 months for 18 months

9. Repeat 24h urine only required for patients with ≥ 200 mg/24h of M-protein at screening

10. Women of childbearing potential only; 2 negative tests are required within 14 days before study drug dosing on C1D1 of consolidation

11. Bone marrow aspirate and core biopsy – differential required; Cytogenetics, and fluorescent *in situ* hybridization (FISH) studies performed per institutional guidelines.

12. See Section 9.0

13. Not required on C1D1 if screening/restaging visit occurred within 28 days prior

14. C1-C4 then every 3 cycles thereafter (i.e., C7, C10, C13 ...)

15. A telephone call to assess OS and PFS can be made in lieu of a physical exam

16. Cycle 13 for all patients. Cycle 25 and 37 also required for patients in suspected or confirmed CR/sCR at that time.

17. See Appendix D. Patient to complete following each cycle of study treatment (consolidation and maintenance).

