11.9 Reporting to Millennium

AEs may be spontaneously reported by the patient and/or in response to an open question from study personnel or revealed by observation, physical examination, or other diagnostic procedures. Any clinically relevant deterioration in laboratory assessments or other clinical finding is considered an AE. When possible, signs and symptoms indicating a common underlying pathology should be noted as one comprehensive event. For serious AEs, the investigator must determine both the intensity of the event and the relationship of the event to study drug administration.

AEs which are serious must be reported to Millennium Pharmacovigilance (or designee) from the first dose of study drug through 30 days after administration of the last dose of ixazomib. Any SAE that occurs at any time after completion of ixazomib treatment or after the designated follow-up period that the sponsor-investigator and/or sub-investigator considers to be related to any study drug must be reported to Millennium Pharmacovigilance (or designee). In addition, new primary malignancies that occur during the follow-up periods must be reported, regardless of causality to study regimen, for a minimum of three years after the last dose of the investigational product, starting from the first dose of study drug. All new cases of primary malignancy must be reported to Millennium Pharmacovigilance (or designee).

Regardless of expectedness or causality, all SAEs (including serious pretreatment events) must also be reported in English to Millennium Pharmacovigilance (or designee). Fatal

and life threatening SAEs must be reported within 24 hours of the sponsor-investigator's observation or awareness of the event, and all other serious (non-fatal/non life threatening) events must be reported within 4 calendar days of the sponsor-investigator's observation or awareness of the event.

US and Canada
Toll-Free [contact]
E-mail: [contact]

If a woman becomes pregnant or suspects that she is pregnant while participating in this study, she must inform the investigator immediately and must permanently discontinue bortezomib. A Pregnancy Form must be requested, completed, and faxed to Millennium Pharmacovigilance. The pregnancy must be followed for the final pregnancy outcome.

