11.10 Timeframe for Reporting Required Events

Adverse events will be collected from first dose of study treatment through the end of study visit.

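### Maintenance adverse events are compared by randomised arm under ITT despite two-way crossover, so the comparison does not estimate each drug's tolerability

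*Combined protocol and SAP*

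**What the plan says.** Section 15.3 (Data Analysis) treats the two phases differently. For consolidation it defines a safety population by treatment received: anyone given one or more doses of IRD. For maintenance it states a single rule: "Data analysis for maintenance portion will be performed following the intent-to-treat (ITT) principle". The same paragraph then turns to toxicity: "The distributions of responses and adverse events across two arms will be summarized using contingency tables", with a Chi-square or Fisher's exact test. No maintenance safety population is defined.

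Crossover is open in both directions. Section 5.3.2: "If ixazomib maintenance is discontinued, crossover to the lenalidomide maintenance arm can occur if permission is granted by the Principal Investigator". Section 5.3.3: "If lenalidomide maintenance is discontinued, crossover to the ixazomib maintenance arm can occur if permission is granted by the Principal Investigator". Both sections keep crossed patients under protocol follow-up. Neither gives a cap or an expected rate.

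Section 11.10 sets the collection period: "Adverse events will be collected from first dose of study treatment through the end of study visit". Note 7 to the Study Calendar (section 8.0) times that visit from the last dose of study drug(s), so collection does not stop at crossover.

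Section 5.1 adds another group. Patients who stop ixazomib or lenalidomide for toxicity during consolidation are not randomised and go by preference to the other arm.

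**The concern.** ITT suits the efficacy comparison. Tolerability is a different question: what happens to patients while they take each drug. Under the rule as written, a lenalidomide event in a patient who has left ixazomib is entered in the ixazomib column, and the reverse. Nothing in the plan cuts the comparison at crossover or assigns later events to the drug being taken.

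That ixazomib maintenance is well tolerated is a stated hypothesis (section 1.4.1). Toxicity between the arms is part of secondary objective 3 (section 2.2), and the results are meant to inform a phase III study (section 1.4). If crossover is similar in the two arms, the error favours a finding of similar tolerability.

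Two features add to the problem. Maintenance is open-ended, and a table of patients with and without an event ignores time on drug. The non-randomised patients of section 5.1 have no randomised arm, so ITT does not say where their events belong.

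**Working it through.** The documents give no rate, power or sample size for the maintenance toxicity comparison, so there is no stated figure to reproduce. The check is an illustration.

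**Inputs**
- From the documents: 110 evaluable patients per arm (section 15.1), and neutropenia on oral single-agent ixazomib in 29 of 201 patients, or 14% (Table 1-2, section 1.2.5).
- Assumed: 30% on lenalidomide (40% as an alternative), crossover shares of 10% to 40%, a two-sided alpha of 0.05, crossing independent of earlier events, and the full event rate of the second drug after crossing.

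**Formula.** Let pI and pL be the true proportions with the event on each drug, and cI and cL the shares crossing from each arm. By randomised arm:
- ixazomib arm = pI + (1 - pI) × cI × pL
- lenalidomide arm = pL + (1 - pL) × cL × pI

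**Equal crossover.** With cI = cL = c, the difference is (pL - pI) + c[(1 - pL)pI - (1 - pI)pL] = (1 - c)(pL - pI).

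At c = 20%: ixazomib arm 0.14 + 0.86 × 0.20 × 0.30 = 0.1916; lenalidomide arm 0.30 + 0.70 × 0.20 × 0.14 = 0.3196; difference 0.128.

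Power is Φ{[d - 1.96√(2p̄(1 - p̄)/n)] / √([p1(1 - p1) + p2(1 - p2)]/n)}, where d is the observed difference, p1 and p2 are the two arm proportions, p̄ is their mean and n = 110. At c = 20% this is Φ{(0.128 - 1.96 × 0.0588)/0.0582} = Φ(0.219), or 59%.

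| c, both arms | Ixazomib arm | Lenalidomide arm | Difference (points) | Power |
|---|---|---|---|---|
| 0% | 14.0% | 30.0% | 16.0 | 82% |
| 10% | 16.6% | 31.0% | 14.4 | 71% |
| 20% | 19.2% | 32.0% | 12.8 | 59% |
| 30% | 21.7% | 32.9% | 11.2 | 46% |
| 40% | 24.3% | 33.9% | 9.6 | 35% |

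With lenalidomide at 40%, the true 26.0 points become 23.4, 20.8, 18.2 and 15.6 at c = 10%, 20%, 30% and 40%.

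**Unequal crossover.** The direction is no longer fixed.
- 14% v 30%, 40% crossing from ixazomib only: 0.14 + 0.86 × 0.40 × 0.30 = 0.243 against 0.30, so 5.7 points remain of 16.0.
- 14% v 30%, 40% crossing from lenalidomide only: 0.30 + 0.70 × 0.40 × 0.14 = 0.339 against 0.14, so 16.0 points become 19.9.
- Both drugs truly 25%, with 30% crossing from ixazomib and 10% from lenalidomide: 0.25 + 0.75 × 0.30 × 0.25 = 0.306 against 0.25 + 0.75 × 0.10 × 0.25 = 0.269. This is a false difference of 3.8 points.

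**Dropping independence.** Suppose 20% cross in each arm, taken first from patients who have already had the event. On ixazomib, 14 of the 20 points of crossers are already counted, so the arm shows 0.14 + 0.06 × 0.30 = 0.158. On lenalidomide all 20 points are already counted, so the arm stays at 0.30. The difference is 14.2 points, not 12.8: the error is smaller but still present.

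**The case against.** A table by randomised arm is a legitimate summary of a strategy (start on one drug, with a switch allowed). The comparison is secondary and pilot, and section 15.1 says the study is not powered for non-inferiority or superiority between the maintenance arms. Crossover may be uncommon: it needs permission, and section 5.7 takes patients off study for progression and for adverse events that rule out further study drug. An event that makes a patient stop the first drug is still charged correctly. The data may also allow a later repair: section 6.0 asks for toxicities to be attributed to a specific drug where possible, section 11.1.1 provides for attribution, section 10.0 has a dosing form each cycle, and Appendix E asks about both drugs.

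All of this stands as a limit on importance, and it makes the gap one of prespecification rather than lost data. It does not change the comparison that section 15.3 specifies, which remains by randomised arm with events on both drugs combined.

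A reader might also infer that the patients who cross early are those with the most toxicity. Sections 5.3.2 and 5.3.3 give no reasons for discontinuation, so this is not shown.

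A reader might also see a conflict in the adverse event cut-offs, because section 11.9 runs serious event reports "through 30 days after administration of the last dose of ixazomib" while section 11.10 stops at the end of study visit. The first governs reporting to the manufacturer and the second general collection. The visit rule is the same in both arms, so this shows neither a contradiction nor a between-arm bias.

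**Conclusion.** The point holds as a defect in section 15.3. Followed as written, the plan charges second-drug events to the first drug, and the resulting contrast does not estimate the tolerability of either. It is worth correcting, but it concerns a secondary, pilot comparison and leaves the primary objective untouched.

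The (1 - c) result is exact only for equal crossover, with crossing independent of earlier events and the second drug acting at its full rate. Two stronger readings are tempting. One is that the difference is certainly diluted. The unequal cases rule that out, and the defensible statement is misattribution of uncertain direction. The other is that a definite share of the signal, such as a third, is lost. That needs crossover shares that the documents do not give, so every magnitude here is illustrative.

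**What to change.** In section 15.3:
- Restrict ITT to maintenance efficacy.
- Define the maintenance safety population as patients with at least one maintenance dose, analysed by drug received.
- Make the main comparison in randomised patients on their first maintenance drug, counting adverse events up to crossover or to a stated window after the last dose of that drug.
- Report post-crossover events separately, under the drug taken at onset.
- Add exposure-adjusted rates, because treatment is open-ended.
- Keep the by-randomised-arm table as supportive. It is also a useful check because time on the first drug may itself depend on toxicity.
- Tabulate the non-randomised patients of section 5.1 separately. They were selected by earlier toxicity and should not be pooled into the randomised comparison.

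The cost is SAP wording and modest extra programming. The sponsor should first confirm that the case report forms capture event onset and dosing dates, because section 10.0 lists forms by name and does not show their fields. No treatment or eligibility rule changes.
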